Quality in the data collected by the oxygen consumption monitor will be ensured by a self-test at startup according to the manufacturer's instructions. Further, anesthesiologist and respiratory care staff will be instructed to monitor for the degree of air leak from the respiratory system by calculating the difference between inspiratory and expiratory measured tidal volumes. If the airleak exceeds this value, air may be added to the tracheal tube cuff. We have shown that when this difference is <15%, VO_2 data are accurately measured in newborns.²⁴ Further, an absence of end-tidal CO_2 data will be used as a signal of an endotracheal tube disconnection and possible suctioning event. VO_2 measurements are known to be unstable for several minutes following suctioning²⁸, so we will exclude VO_2 data for 10 minutes following any ETT disconnect from analyses.

Figure 6. The oxygen-based monitoring and data collection systems utilized for this study are attached to a rolling pole which can be placed anywhere around the patient and easily moved for convenience and safety.

Data within the SVC monitoring probe will be ensured by an in vitro calibration prior to probe insertion. When ever the treating team sends a venous blood gas from the central venous line, the co-oximetry value will be entered into the machine and used to recalibrate the probe in real-time.

Quality in the transfer of data from the medical record to the spreadsheet will be ensured by an independent review of the primary data by a second member of the study team. Furthermore, when possible, the fields for data entry will contain 'Data Validation' functions (i.e. value will turn red if outside expected limits, and hard stops will be inserted for physiologically impossible values). Additionally, drop down lists will be utilized when possible to minimize data entry errors.

Data Analysis Plan

Patients will be divided into patients who do and do not experience PLOC. All variables will be normalized to hours prior to bypass, bypass time and hours post-bypass time, such that all data for a specific post-bypass time will be aligned between patients. All weight-dependent variables will be normalized to preoperative body weight. Using GraphPad Prism, each variable will be entered into a different column for analysis.

Simple analyses (e.g. mean, standard deviation, tests for normality) will be completed within GraphPad. With regards to the primary endpoint, VO₂ measurements will be analyzed for 120 minutes prior to a PLOC event in cases, and a randomly selected 120 minute period in controls. Values will be compared between cases and controls using generalized estimating equations (GEEs) to account for the correlation of multiple measurements within the same patient and to compare means between cases and controls. A post-hoc broken stick analysis will be used to determine the time prior to the event at which the VO₂ changed in each patient experiencing an event. Data for HLHS and dTGA patients will be pooled together.

More complex analyses will be completed by a collaborating company called Etiometry (including [name] and [name], co-investigators on this study), with whom the PI and others within the CICU have an established relationship. Deidentified information will be sent to the company, who will complete further analyses.

Power Calculations and Sample Size

The measured oxygen consumption in neonates following S1P has been described as 86 ± 16 mL/min/m^{2.22}. A sample size that includes 3 cardiac arrest events would allow us to detect a true decrease of 53 mL/min/m² in oxygen consumption with 90% power and a significance level of 0.05 (two tailed). Based on the significant change in VO₂ noted in the animal studies preceding cardiac arrest, we do not feel that this number is an unreasonable number. In order to collect 3 patients meeting the endpoint, we predict that we will require 20 patients undergoing S1P.

Risks and Discomforts

Because this is a prospective, observational study which we do not expect to change the standard of care, the risks associated with this study are really those of the standard

of care. The VO_2 measurements will be taken using an FDA-approved device which samples gas from the side of the tracheal tube of each patient. In reality, the adapter used by the study monitor is smaller and lighter than than used in our current capnographs, so the risk of accidental endotracheal tube removal should be the same or lower.

The second standard intervention used here which imposes risk is the insertion of an internal jugular venous catheter, which again is standard practice in newborns undergoing these procedures. The theoretical risks of this FDA approved device are no different from standard catheters, which include bleeding, infection and thrombosis. To address these, the staff within the CVP at BCH utilize an insertion bundle and antibiotic coated catheters, which will be a practice which is unchanged in this study. As per routine in the CICU, the catheters will be infused with a Heparin infusion at 10 Units/kg/ hour through one of the two ports of the line, which will decrease any risk of thrombus formation. The catheters are additionally coated with AMC Thromboshield (a coating containing both Heparin and antimicrobials), which will further decrease the risks of both infection and thrombus formation.

Potential Benefits

Potential Direct Benefits

Because this is a prospective observational study, the measurements are not intended to change the standard of care by which these patients are treated. However, there are several possible direct benefits to patients:

- *Decrease in venous blood sampling.* It is possible that due to the indwelling oximeter that the care team will require fewer blood samples to be tested for SVC saturations. This could potentially decrease the blood loss associated with blood sampling and diminish the risk of infection (which is associated with the number of times a line is entered).
- *Improved assessments of Q_p/Q_s .* As discussed in the background section, the ratio of blood flow to the lungs to that of the body is a vitally important number in the care of patients with HLHS. In the CICU, it is common practice to make changes in patient management based on this value, although the value itself is quite often inaccurately assessed.³ The primary unmeasured variable in the calculation of this ratio is the SVC saturation. The ability to constantly and accurately monitor this value, in combination with arterial saturations based on pulse oximetry, may vastly improve the quantification of the Q_p/Q_s ratio and better inform management decisions at the bedside for critically ill neonates.
- *Earlier recognition of circulatory failure.* Regardless of a patient's underlying anatomy, the difference in oxyhemoglobin saturation between a patient's systemic arterial and venous circulations represents the adequacy of end organ oxygen delivery (reference Figure 1 above). It is possible that by continuously monitoring both the systemic arterial and venous oxyhemoglobin saturations (the former by pulse oximetry), that the treating team will be able to more rapidly identify evolving circulatory failure. There are many interventions which could be utilized

by the care team prior to PLOC which may improve patient outcomes as a result of and in response to this single factor.

Potential Indirect Benefits

This study has the potential to significantly improve the way that newborn patients (and others) are monitored in the postoperative period. Currently, the circulation of these patients are assessed indirectly, using surrogate measures (using cNIRS, and intermittent lactate and SVC saturations measurements) and vital signs. Because our definitive treatment for refractory circulatory failure is ECMO, and because ECMO itself can cause life-threatening complications, it is extremely challenging to determine which patients are at a higher risk of death or organ injury from inadequate DO_2 compared to the risks of these complications from ECMO. It is possible that if the primary hypothesis of the study, that critically ill patients in the CICU exhibit pathologically supply dependent oxygen consumption, that VO_2 monitoring could add significant, continuous, noninvasive information to the care of newborns during their highest risk period. For the short term, this could permit treating teams to measure the effects of their interventions on oxygen delivery (e.g. addition of inotropes, blood transfusions, clips on shunts) and inform these decisions. For the long-term, it is possible that VO_2 and continuous SVC saturation monitoring could inform a predictive algorithm for the sensitive and specific prediction of which patients suffer from recalcitrant circulatory insufficiency, those which may be at risk for PLOC, and who would benefit from ECMO support. If true, this would likely significantly improve the survival rate and neurologic outcomes of newborns with congenital heart disease.

Privacy and Confidentiality Provisions

Privacy Provisions

As mentioned above, patients will be identified by the PI or one of his designees by a regular, systematic review of the census and diagnosis list in the Cardiac Intensive Care Unit at Boston Children's Hospital. Therefore, patients will not be approached for consent unless they meet full inclusion criteria and their treating team assents. Only parents, who will be aware of their child's diagnosis of congenital heart disease, will be approached about the study. None of the patient's comorbidities will be discussed with the patient or family as part of this study.

Confidentiality Provisions

All data will be tracked using unique patient identifiers (UPI). Links between UPI and name and medical record number will be kept in a password-protected file on the PI's computer, and as a printed backup in the PI's locked office. Both of these will be destroyed following data analysis. All primary data will be saved on a hard drive maintained in the locked office of the PI. All data will be deidentified using the UPI as the only identifier. All data files will be password protected, and only study investigators will have access to this password. All files sent via email will be sent with encryption.

References

1. Schumacker, P. T. & Cain, S. M. The concept of a critical oxygen delivery. *Intensive Care Medicine* **13**, 223–229 (1987).
2. Ronco, J. J. *et al.* Identification of the critical oxygen delivery for anaerobic metabolism in critically ill septic and nonseptic humans. *JAMA* **270**, 1724–1730 (1993).
4. Ravishankar, C. *et al.* Association of impaired linear growth and worse neurodevelopmental outcome in infants with single ventricle physiology: a report from the pediatric heart network infant single ventricle trial. *J. Pediatr.* **162**, 250–256.e2 (2013).
5. Sherwin, E. D. *et al.* Extracorporeal membrane oxygenation after stage 1 palliation for hypoplastic left heart syndrome. *J Thorac Cardiovasc Surg* **144**, 1337–1343 (2012).
6. Kane, D. A. *et al.* Rapid-response extracorporeal membrane oxygenation to support cardiopulmonary resuscitation in children with cardiac disease. *Circulation* **122**, S241–8 (2010).

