exhibited a pronounced decrease in their measured VO_2 , a pattern which was not present in treated animals which did not experience subsequent hemodynamic instability (**Figure 3**). Having seen this pattern consistently in approximately $n=40$ animal experiments (weight range 2.5-4 kg), we hypothesize that in critically ill patients, VO_2 may decrease below the critical DO_2 and exhibit measureable, even striking, decreases prior to hemodynamic decompensation takes place. If this hypothesis is true, quantification of VO_2 may represent a new 'vital sign' which represents end organ oxygen delivery in critically ill patients. Identification of patients with pathologically supply dependent VO_2 may permit definitive interventions to take place, e.g. initiation of extracorporeal life support, prior to a life-threatening PLOC.

Study Objectives

Specific Aim 1. To demonstrate that oxygen consumption (VO_2) and superior vena cava (SVC) saturations can be safely and precisely measured continuously in newborns undergoing surgery for hypoplastic left heart syndrome (HLHS) or d-transposition of the great arteries with an intact ventricular septum (d-TGA/IVS).

Hypothesis: Measurement of these oxygen-based parameters will not be associated with an increased incidence of equipment-related adverse events (e.g. line displacements, inadvertent extubations) and will lead to precise and reproducible measurements of these important parameters.

Specific Aim 2. To determine whether postoperative loss of circulation (PLOC, defined as cardiac arrest requiring CPR, ECMO cannulation, or causing death) in these patients are associated with a change in oxygen consumption or SVC saturation prior to the event.

Hypothesis: PLOC will be associated with significant decreases in both oxygen consumption and SVC saturations for at least 10 minutes prior to the onset of cardiac arrest.

Specific Aim 3. To determine whether the addition of the oxygen-based measurements to standardly measured parameters (i.e. vital signs, near-infrared spectroscopy

[figure not shown]

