In lieu of the standard Cook Medical catheter, the treating team will place a similar FDA-approved catheter, but which is fitted with a fiberoptic sensor which continuously records the oxyhemoglobin saturation of the blood to which it is exposed. The catheter is 4.5 French, 5 cm in length, has two lumens, and is Heparin bonded (PediaSat catheter, Edwards LifeSciences, Model# XT245HK, see **Figure 5**). The catheter comes with a sterile percutaneous insertion kit. As above, all cardiac intensivists, cardiac anesthesiologists and CICU nursing staff will receive a formal training on the insertion and care of this catheter by the company representative ([name]). Prior to insertion, the catheter will be calibrated using an in vitro solution which comes with the catheter. For those familiar with the device, this process will add 2-3 minutes to the insertion time. Following insertion of the catheter, the device will be attached to the study monitor (Datex Ohmeda Critical Care Monitor, GE Healthcare) via a specialized cable. The catheters will be paid for by the PI.

Figure 5. The PediaSat catheter to be used in this study is functionally the same as catheters routinely used in the perioperative care of newborns with CHD except that it is fitted with a fiberoptic probe at its tip which continuously reads SVC saturation.

In the opinion of the study team, the SVC saturation is a clinically useful piece of data which is routinely used at BCH in the management of patients. Because the device readings have been shown to correlate well with oximetric readings from venous blood, the SVC saturation will be continuously displayed on the study monitor for clinicians to use at their discretion for the duration of the study.

The study will end following the first postoperative extubation or removal of the central venous catheter, whichever occurs last.

Endpoints/Outcomes

Primary Outcome. The primary outcome being measured will be a composite endpoint of PLOC, including the need for CPR, the need for ECMO in the setting of CPR, or death.

Secondary Outcomes. Because Aim 3 of this study is to determine whether the aforementioned oxygen-based measurements add to the predictive power of the data standardly used to assess patients, there will be a substantial amount of data gathered, which is outlined below.

- Oxygen-based parameters unique to this study

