- Chest explorations and operative interventions performed at the bedside (e.g. clipping of BTS or Sano shunt) will be recorded each day from a review of the medical record, discussion with the primary team (including the bedside nurse) and the notes within the medical record.
 - Blood loss from chest tubes (in mL/kg each hour) and blood product administrations (including the blood products given and the times at which they are given) will be recorded from the medical record each day.
 - Sedatives and paralytics are routinely used and also affect oxygen consumption.
 - Diuretic medications are also routinely used, can affect preload.
 - Arrhythmias and
 - Other clinical parameters
 - Urine output is a crude marker of intravascular volume and end organ oxygen delivery.
 - The presence of enteral feedings, the rate of feedings and the caloric densities will also be recorded, as these may affect a patient's systemic vascular resistance.
 - Operative characteristics
 - Full preoperative and postoperative anatomic diagnoses
 - Residual anatomic defects
 - Total pump time, cross-clamp time, circulatory arrest time, regional perfusion time, minutes of continuous and modified ultrafiltration, blood products administered on bypass

Data Collection Methods, Assessments and Schedule

Outcome measurements

The majority of the endpoints presented above are routinely collected within the medical record as a part of patient care. Therefore, the majority of the data will be abstracted directly from the medical record and into a spreadsheet for data analysis by a member of the study team during each day for the duration of the study. The PI employs two full-time technicians within his lab who will assist with this labor intensive process.

- The oxygen-based measurements which are central to this study, including VO_2 , SVC saturation, as well as all ventilatory parameters listed above will be saved to a computer program (S5 Collect, GE Healthcare) attached to the patient's monitor. This program saves data in time stamped fashion Q1 second.
- Time-stamped vital sign data listed above will be exported daily from the hospital's in situ T3 program (Arcadia Solutions).
- The labs, treatments and other clinical parameters (see previous section) will be extracted in time-stamped fashion from the medical record each day by a member of the study team.

Patient variables

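### Aim 1 promises precise, reproducible and continuous VO2 measurement, but no planned analysis estimates VO2 repeatability or usable recording time

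*Combined protocol and SAP*

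**What the plan says.** All places are in the combined protocol and SAP.

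- **Study Objectives, Specific Aim 1.** The aim is to demonstrate that VO2 and SVC saturation "can be safely and precisely measured continuously in newborns undergoing surgery" for HLHS or d-TGA/IVS. The hypothesis has a safety part (no excess of equipment-related events) and a measurement part: monitoring "will lead to precise and reproducible measurements of these important parameters". The Project Summary states this aim for oxygen consumption alone.
- **Endpoints/Outcomes.** "The primary outcome being measured will be a composite endpoint of PLOC". The secondary outcomes are introduced through Aim 3: "there will be a substantial amount of data gathered, which is outlined below". The list that follows names variables to collect. None is a measure of repeatability or completeness.
- **Data Collection Methods.** VO2, SVC saturation and the ventilatory parameters go to a data-capture program: "This program saves data in time stamped fashion Q1 second".
- **Quality control methods.** There is a start-up self-test and a check of the gap between inspired and expired tidal volume. Earlier work is cited for accuracy when that gap is under 15%. VO2 data are dropped for 10 minutes after any tube disconnect.
- **Data Analysis Plan.** "Patients will be divided into patients who do and do not experience PLOC". "Simple analyses (e.g. mean, standard deviation, tests for normality) will be completed within GraphPad". A GEE then compares case and control VO2 over 120-minute periods, and a post-hoc broken-stick analysis dates the change in infants with an event. Further analyses go to a collaborating company, with no content given.
- **Parameters for discontinuation of the research.** Adverse events are compared with a retrospective control. This is the only stated comparison that bears on Aim 1, and it concerns safety.

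**The concern.** Aim 1 is worded as something this study will show. Its measurement part makes two claims about VO2 that need estimates: that repeated readings agree (precise, reproducible), and that readings are available most of the time (continuous). Followed as written, the plan produces neither estimate, so that half of the aim has no planned answer from the study's own data.

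The gap also touches Aim 2. The broken-stick analysis looks for a change point in each infant with an event, and the sample size rests on 3 such events. Whether a fall in one infant's trace is more than the monitor's ordinary variation depends on the within-infant SD, which nobody is asked to estimate. The Aim 2 hypothesis concerns at least the last 10 minutes before arrest. That is exactly the length of the gap that one disconnect leaves in the VO2 record.

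**Working it through.** **Is there a plan figure to reproduce?** No. The documents give no value, target or sample-size basis for VO2 precision or completeness. The power statement (86 ± 16 mL/min/m2, fall of 53, 3 events) belongs to Aim 2.

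**Step 1. Compare each planned item with what Aim 1 needs.**

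| Planned item | Within-infant repeatability? | Usable time? |
|---|---|---|
| Mean, SD, normality tests | No, components are mixed | No |
| GEE, cases v controls | No, within-infant correlation is allowed for but no repeatability is reported | No |
| Broken stick, event infants | No, it dates a change | No |
| Outsourced analyses | Not specified | Not specified |
| Self-test, leak check, 10-minute exclusion | No, these are data-quality rules | No, lost time is not tallied |

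For leak above the limit, the text gives a bedside response but no rule to exclude or count the affected VO2 data.

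**Step 2. Why a pooled SD cannot stand in.** For readings averaged over the same interval, with independent components:

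pooled SD² = noise SD² + (between-infant and real-change SD)²

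Take a pooled SD of 16, borrowed from the power section only as an example (16² = 256):

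- noise SD 5: the remainder is √(256 − 25) = 15.2
- noise SD 10: the remainder is √(256 − 100) = 12.5
- noise SD 15: the remainder is √(256 − 225) = 5.6

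The same pooled SD fits a quiet monitor and a noisy one.

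**Step 3. What the missing SD would decide in one infant.** Smallest readable change between two 10-minute means = 1.96 × √2 × within-infant SD = 2.77 × SD. The SDs are assumed:

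- SD 5: 13.9, about 14 mL/min/m2
- SD 10: 27.7, about 28 mL/min/m2
- SD 15: 41.6, about 42 mL/min/m2

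**Step 4. Time lost to the 10-minute rule alone.** The disconnect rates are assumed, with no overlap between exclusions:

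- one per 4 hours: 10/240 = 4.2%
- one per hour: 10/60 = 16.7%
- one in a 120-minute analysis window: 10/120 = 8.3% of that window

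Loss to leak or dropout would come on top.

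**Step 5. Could the planned sample answer the question?** Yes, to a useful degree.

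- *Within-infant SD*, two stable windows per infant (assumed). The 95% limits are √(df/χ²) times the estimate, with df equal to the number of infants: 0.82 to 1.28 times at n = 40, and 0.77 to 1.44 times at n = 20.
- *Mean usable fraction.* The 95% half-width is t × SD/√n. For an assumed between-infant SD of 0.10 to 0.30 it is 0.03 to 0.10 at n = 40, and 0.05 to 0.14 at n = 20.

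**The case against.** The strongest reply is that precision is already established. The background says that several devices are precise in newborns after heart surgery and that this device was validated against mass spectrometry. The quality-control section cites accuracy under 15% leak. These statements count as a stated basis and cannot be checked from here. They are still not an estimate from this study, which is what Aim 1 promises. Judged by titles only, the reference given for the mass-spectrometry claim is a laboratory validation of a module with a different name, and the reference for the leak claim concerns children after Fontan surgery. The titles do not settle what those papers contain.

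Several stronger readings are tempting, and the documents do not support them:

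- *Aim 1 would be declared met with no evidence.* No section says how Aim 1 will be judged, and prior validation is cited.
- *Every VO2 analysis is a comparison by PLOC status.* The descriptive analyses are not restricted in that way, and the outsourced work is undefined. Because it is undefined, it cannot be credited either.
- *Monitor noise would hide the fall of 53 mL/min/m2.* Even the largest assumed SD gives 42. The two figures also differ in kind: 53 is a group-level fall detectable with 90% power, while 42 is a limit for two readings in one infant.
- *Lost time threatens the aims.* The 4% to 17% rests on assumed disconnect rates.

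It is also fair that the main Aim 2 comparison is of group means, that VO2 is hidden from clinicians, and that the estimates could be added later from stored data. These points limit the urgency but do not supply the missing analysis.

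**Conclusion.** The concern holds in this form: Aim 1 undertakes to demonstrate precise, reproducible and continuous VO2 measurement, and no planned within-study analysis estimates VO2 repeatability or the share of intubated time with usable VO2. The planned mean and SD cannot fill the gap, and no criterion for Aim 1 is given.

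The gap is one of substance as well as detail, because one half of a stated aim is left without an answer. It should be closed before analysis. It does not undermine the primary endpoint or the Aim 2 group comparison. Its practical size is unknown: the SDs, disconnect rates, number of windows and spread of usable time used above are all assumptions and are not evidence of harm.

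**What to change.** Add an Aim 1 analysis of VO2 on all infants, using data already recorded.

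1. **Usable-time fraction.** Numerator: seconds with VO2 present, inspired-expired leak below 15%, and outside the 10-minute post-disconnect exclusion. Denominator: seconds intubated and off bypass. Report it with reasons for loss, overall and for the 120 minutes before PLOC. State how time on ECMO is handled.
2. **Repeatability.** Report the within-infant SD and CV of 10-minute VO2 means, in stretches with no disconnect and no recorded change in inotrope, sedative, paralytic or FiO2. Do this for adjacent windows and for windows further apart within 120 minutes, since neighbouring windows share slow drift. Give a cluster-bootstrap confidence interval, resampling infants. Describe the result as an upper bound on device noise, because unrecorded physiological change such as activity remains.
3. **Smallest readable change.** Report 1.96 × √2 × SD and use it to interpret individual falls in the broken-stick analysis. Do not set it against 53 mL/min/m2.
4. **Criterion.** Before analysis, state a criterion for items 1 and 2, and base the Aim 1 VO2 conclusion on them.

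VO2, FiO2 and both tidal volumes are saved every second. Drug changes are to be taken from the record with time stamps. The working spreadsheet is laid out by hour, so the stable stretches should be built from the time stamps.

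Cost: one paragraph in the analysis plan and a little more programming, with no new patients, procedures or change in care. The downside is that the Aim 1 conclusion may turn out less favourable.
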